#### 10.2.3 Subgroups

The study is not powered to draw conclusions from subgroup analyses. However, exploratory analyses will be conducted to examine the consistency of the treatment effect in the primary endpoint for the below subgroups:

- Sex (Male vs Female)
- Stage of disease (Stage 1 to 3, Stage 4 or recurrent disease)
- Prior or Concurrent Bevacizumab use (Yes, No)
- Number of previous chemotherapy cycles ( $\leq 2$ ,  $> 2$ )
- Type of chemotherapy regimen (FOLFOX, FOLFIRINOX, FOLFOXIRI, CAPEOX)
- Baseline platelet count ( $< 50 \times 10^9/L$ ,  $\geq 50 \times 10^9/L$ ) (stratification factor)
- Tumor type (Gastrointestinal, Pancreatic Colorectal) (stratification factor)

#### 10.2.4 Handling of Missing and Incomplete Data

For primary analysis **on the thrombocytopenia-induced dose modification**, subjects with complete missing visits (missing chemotherapy and none of the protocol specified

assessments are performed) or partial visits (missing chemotherapy but some of the protocol specified assessments are performed) without platelet count assessment for cycle 2 and/or cycle 3 are imputed as having thrombocytopenia-induced dose modification in cycle 2 and/or cycle 3. **Subjects with missing chemotherapy but having platelet count assessment within 2 days of the planned chemotherapy start or chemotherapy discontinuation will be determined by the adjudication committee.**

Potential missing visits or missing assessments may result from below reasons:

- Death
- Early discontinuation of chemotherapy
- Consent withdrawal or lost to follow up

### **10.3 Statistical Analyses**

The statistical analysis plan will be developed and finalized before database lock. Below is a summary of the timing and methods for the planned statistical analyses. To preserve study integrity, the final analysis will be conducted and reported following the end of study, as defined in Section 5.3.1.

#### **10.3.1 Planned Analyses**

##### **10.3.1.1 Interim Analysis and Early Stopping Guidelines**

**One interim futility analysis will be performed at approximately 81 subjects completing three cycles of chemotherapy. The primary endpoint, which is the proportion of subjects with no thrombocytopenia-induced chemotherapy dose modification in the second and third cycles of the planned on-study chemotherapy regimen, will be analyzed at the interim analysis. Dose modification assessments will be based on the central review by the independent adjudication committee. The futility boundary for the primary endpoint is p-value of 0.438, which corresponds to an OR of 1.086. The study may be stopped for futility if the non-binding futility boundary is crossed.**

**Due to slow enrollment, there will be no enrollment pause during the interim analysis. An independent Data Monitoring Committee (DMC) will perform the futility analysis. The DMC will make recommendation to Amgen regarding the continuation of the study. The DMC will be supported by an independent biostatistics group which is responsible for preparing reports. Details regarding**

**the responsibilities of the DMC and the independent biostatistics group will be described in the DMC Charter.**

#### **10.3.1.2 Primary Analysis**

The primary analysis will be performed at the primary completion date. The primary completion date is defined as the date when the last subject is assessed or receives an intervention for the final collection of data for the primary endpoint. Based on the definition above, the primary completion date is either the date when the status (information on whether a given on-study chemotherapy cycle was administered as planned, administered at a modified dose, delayed, omitted or discontinued) of the third cycle of the planned on-study chemotherapy regimen is assessed on the last subject or the last subject ends the last dose of investigational product plus 30 days, whichever occurs later. The data that are collected up to the primary completion date will be cleaned and locked for the primary analysis purposes. The study will be unblinded at the primary analysis.

If the study concludes prior to the primary completion date originally planned in the protocol (ie, early termination of the study), then the primary completion will be the date when the last subject is assessed or receives an intervention for evaluation in the study (ie, last subject last visit).

#### **10.3.1.3 Final Analysis**

When the last subject in the trial completes LTFU at 1 year after the last dose of investigational product, the final database will be locked for the final analysis.

### **10.3.2 Methods of Analyses**

#### **10.3.2.1 General Considerations**

The primary efficacy endpoint will be compared between the romiplostim and placebo groups at the significance level of 0.05 using a 2-sided test. If statistical significance is achieved for the primary endpoint in favor of romiplostim, **the following secondary efficacy endpoints will be tested using a fixed sequence hierarchical testing procedure to control the family-wise Type I error rate below 2-sided 0.05 level.**

**The family of hypotheses is ordered as follows:**

- the depth of platelet count nadir from the start of the first on-study chemotherapy cycle through the end of the treatment period
- the time to first platelet response, defined by platelet count  $\geq 100 \times 10^9/L$ , in the absence of platelet transfusions during the preceding 7 days. Subjects who did not achieve a response event during the treatment period are censored at their last

platelet count assessment date up to the EOTP or study day 1 if they did not have any platelet assessment

- the duration-adjusted event rate of  $\geq$  grade 2 bleeding events as assessed per CTCAE version 5.0 grading scale
- overall survival
- platelet transfusion(s) during the treatment period
- achieving platelet count  $\geq 100 \times 10^9/L$  at any time after study day 1 to week 4 (ie, 7 days after the planned third dose of investigational product) in the absence of platelet transfusions during the preceding 7 days

**Starting with the hypothesis of platelet count nadir, if any null hypothesis in the sequence is rejected at a 2-sided significance level of 0.05, then the subsequent hypothesis will be tested; if any null hypothesis is accepted, then the subsequent hypotheses will not be tested.**

Summary statistics without formal testing will be provided for other endpoints.

### **10.3.2.2 Efficacy Analyses**

#### **10.3.2.2.1 Primary Endpoint**

Primary endpoint is no thrombocytopenia-induced modification of any myelosuppressive treatment agent in the second and third cycles of the planned on-study chemotherapy regimen. Chemotherapy dose modification in the first cycle of the planned on study chemotherapy regimen will not be counted toward the primary endpoint. Chemotherapy dose modification includes dose reduction, delay, omission, and discontinuation. The proportion of subjects with no thrombocytopenia-induced modification will be provided with a 95% CI for each treatment group. A 2-sided CMH test will be used to compare groups controlling for the stratification factors of tumor type and baseline platelet count. The common odds ratio for romiplostim vs placebo will be estimated along with a 95% CI. The difference in proportions between treatment groups will be provided with a 95% CI. Additional sensitivity analysis will be described in the Statistical Analysis Plan.

#### **10.3.2.2.2 Secondary Endpoints**

##### **10.3.2.2.2.1 Depth of Platelet Nadir**

The first secondary endpoint is the depth of platelet nadir from the start of the first on-study chemotherapy cycle through the EOTP. Linear regression models will be used to compare the mean nadir between the romiplostim and placebo groups. Dependent variables will include the treatment group, the stratification factor of tumor type and baseline platelet count, and the interactions between treatment group and the stratification factors. The normality assumption for linear regression models will be

checked using a normal probability plot of the residuals and the Shapiro-Wilk test (Shapiro and Wilk, 1965). If the data fail to meet the normality assumption, data transformation or a non-parametric method may be considered. The detailed analysis plan will be described in the Statistical Analysis Plan.

#### **10.3.2.2.2.2 Time to Platelet Response**

The time to first platelet response is defined by platelet count  $\geq 100 \times 10^9/L$  in the absence of platelet transfusions during the preceding 7 days. Time to first platelet response will be calculated from the study day 1 to the date of achieving first platelet count  $\geq 100 \times 10^9/L$ . Subjects who did not achieve a response event during the treatment period are censored at their last platelet count assessment date up to the EOTP or study day 1 if they did not have any platelet assessment.

A 2-sided log-rank test stratified by tumor type and baseline platelet count will be performed to determine whether time to first platelet response is significantly different between treatment groups. The hazard ratio of achieving platelet response for romiplostim vs placebo and its corresponding 2-sided 95% CI will be provided using a stratified Cox regression model.

Kaplan-Meier curves for the time to achieving first platelet response will be presented along with Kaplan-Meier **estimates** and 2-sided 95% CIs at specified time points (week 3, week 4, etc) for each treatment group. In addition, Kaplan-Meier quartiles (median, 25th, and 75th percentiles) will be estimated with 2-sided 95% CI, if estimable.

#### **10.3.2.2.2.3 Duration-adjusted Event Rate of $\geq$ Grade 2 Bleeding Events**

Duration-adjusted event rate of grade  $\geq 2$  bleeding events are calculated as total number of events divided by the total duration (per 100-subject-years) from study day 1 until the date of last dose of investigational product plus 30 days. The number of grade  $\geq 2$  bleeding events will be summarized for each treatment group. An Andersen-Gill model (Andersen and Gill, 1982) with a robust variance estimator (Lin and Wei, 1989), stratified by tumor type and baseline platelet count, will be used to analyze recurrent bleeding events and will provide hazard ratio with 95% CI and p-value comparing treatment groups.

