Endpoints: Secondary (3) – Duration-adjusted Event Rate of \geq Grade 2 Bleeding Events

The duration-adjusted event rate (**events/100 subject-years**) is defined as the number of grade ≥ 2 bleeding events, divided by the total duration (in 100 subject-years) that subjects have been on study from study day 1 to the earliest of last dose of IP + 30 days or EOS.

Bleeding events will be recorded on the adverse events case report form (CRF) and graded using the CTCAE version 5.0. Bleeding events will be identified using the narrow search of haemorrhages standardized MedDRA query (SMQ), using the MedDRA version 25.1 or later.

Abbreviations:

- b.events = Bleeding Events (Haemorrhages)
- Status = 1 (recurrence of b.event)
- Status = 0 (no b.event)

Censoring Rules:

- Subject with at least one or more than one “grade ≥ 2 b.events”
 - Subject may report multiple b.events, each b.event will be flagged with “Status = 1”.
 - Subject may report multiple b.events, if any b.event end date is missing then also “Status = 1”.
 - The treatment period from last b.event start date to Min(last dose of IP date+30, Study End date) will be considered as no event period, reported as “Status = 0”
- The subjects who do not report any “grade ≥ 2 b.events”
 - These subjects will be included in analysis with “Status = 0”.

Notes:

Status variable will be assigned considering “Haemorrhages” SMQ only, irrespective of number of other adverse event(s) experienced by subject.

- **Status is the censoring variable which will be utilized into the PHREG.**

Endpoints: Secondary (4) –Overall Survival

Overall survival time will be calculated from study day 1 to death. Subjects who have not died will be censored at their last date of contact.

Endpoints: Secondary (5) – Platelet Transfusion

Platelet transfusions during the treatment period is defined as a subject having at least one platelet transfusion after during study period as recorded on the transfusions CRF.

Endpoints: Secondary (6) – Achieving a platelet count $\geq 100 \times 10^9/L$

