9.1 General Considerations

Continuous variables will be summarized descriptively by the n, mean, standard deviation, median, Q1 (25th percentile), Q3 (75th percentile), minimum, and maximum. The confidence interval and standard error for the mean will also be summarized for efficacy variables that are continuous. Categorical variables will be summarized descriptively by the number and percentage in each category. Missing values will be shown as a separate category. The confidence interval will also be summarized for dichotomous efficacy variables.

Time to event variables will be summarized with hazard ratios, Kaplan-Meier curves, Kaplan-Meier quartiles, the number of subjects at risk, the number of subjects censored, and the number of subjects with events.

Where confidence intervals are provided, these will be 2-sided at the 95% level, unless otherwise specified.

The primary efficacy endpoint will be compared between the romiplostim and placebo groups at the significance level of 0.05 using a 2-sided test. If statistical significance is achieved for the primary endpoint in favor of romiplostim, **the following secondary efficacy endpoints will be tested using a fixed sequence hierarchical testing procedure to control the family-wise Type I error rate below 2-sided 0.05 level. The family of hypotheses is ordered as follows:**

- the depth of platelet count nadir from the start of the first on-study chemotherapy cycle through the end of the treatment period
- the time to first platelet response, defined by platelet count $\geq 100 \times 10^9/L$, in the absence of platelet transfusions during the preceding 7 days.
- the duration-adjusted event rate of \geq grade 2 bleeding events as assessed per CTCAE version 5.0 grading scale
- overall survival
- platelet transfusion(s) during the treatment period
- achieving platelet count $\geq 100 \times 10^9/L$ at any time after study day 1 to week 4 (ie, 7 days after the planned third dose of investigational product) in the absence of platelet transfusions during the preceding 7 days

Starting with the hypothesis of platelet count nadir, if any null hypothesis in the sequence is rejected at a 2-sided significance level of 0.05, then the subsequent hypothesis will be tested; if any null hypothesis is accepted, then the subsequent hypotheses will not be tested.

Summary statistics without formal testing will be provided for other endpoints.

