Appendix A. Code Fragment for Andersen-Gill Model

Duration adjusted bleeding event (Andersen-Gill Approach):

- K is strata for tumor type
- J is strata for baseline platelet count
- Tstart is time of the (k-1) recurrence for visit = k, or the entry time 0 if visit = 1, or the follow-up time if the (k-1) recurrence time does not occur
- Tstop is time of the kth recurrent if visit = k or follow-up time if the kth recurrence does not occur
- Status is bleeding status of Tstop (1=recurrence and 0=censored)
- txgrp is the treatment group variable:
 - active
 - placebo

PROC PHREG covs(aggregate);

Class J K txgrp;

MODEL (Tstart,Tstop)*Status(0)=Txgrp / ties=efron;

Strata K J;

Id usubjid;

Run;

Appendix B. Handling of Dates, Incomplete Dates and Missing Dates**Imputation Rules for Partial or Missing Start Dates**

The reference date for the following rules is the date of first dose[of study drug].

Start Date		Stop Date						Missing	
		Complete: yyyymmdd		Partial: yyyymm		Partial: yyyy			
		< 1 st dose	≥ 1 st dose	< 1 st dose yyyymm	≥ 1 st dose yyyymm	< 1 st dose yyyy	≥ 1 st dose yyyy		
Partial: yyyymm	= 1 st dose yyyymm	2	1	n/a	1	n/a	1	1	
	≠ 1 st dose yyyymm		2	2	2	2	2	2	
Partial: yyyy	= 1 st dose yyyy	3	1	3	1	n/a	1	1	
	≠ 1 st dose yyyy		3		3	3	3	3	
Missing		4	1	4	1	4	1	1	

1=Impute the date of first dose; 2=Impute the first of the month; 3=Impute January 1 of the year; 4=Impute January 1 of the stop year

Note: Note: If the start date imputation leads to a start date that is after the stop date, then do not impute the start date.

Imputation Rules for Partial or Missing Stop Dates

Initial imputation

- **If the month and year are present, impute the last day of that month.**
- **If only the year is present, impute December 31 of that year.**
- **If the stop date is entirely missing, assume the event or medication is ongoing.**

If the imputed stop date is before the start date, set stop date to missing.

If the imputed stop date is after the death date, impute as death date.

Death Dates, Secondary Malignancy Onset Dates, and MDS Onset Dates

If death/malignancy/MDS year and month are available but day is missing:

- If mmYYYY for last contact date = mmYYYY for death/malignancy/MDS date, set death/malignancy/MDS date to the day after the last contact date or EOS date, whichever occurs first.
- If mmYYYY for last contact date < mmYYYY for death/malignancy/MDS date, set death/malignancy/MDS date to the first day of the death/malignancy/MDS month.

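### The gating p-value for grade ≥2 bleeding would, on the SAP's code, be a robust Wald test that falls to effectively zero if every bleed is in one arm

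*Protocol*

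**What the plan says.** Bleeding is third of six secondary efficacy endpoints, after platelet nadir and time to first platelet response and before overall survival. The gate is the same in Protocol 10.3.2.1 and SAP 9.1: "if any null hypothesis in the sequence is rejected at a 2-sided significance level of 0.05, then the subsequent hypothesis will be tested". The primary test must favour romiplostim. For the secondary tests no direction and no minimum number of events is stated.

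Protocol 10.3.2.2.2.3 and SAP 9.5.2.3 give one inferential method: an Andersen-Gill model with robust variance, stratified by tumour type and baseline platelet count, which "will be used to analyze recurrent bleeding events and will provide hazard ratio with 95% CI and p-value comparing treatment groups". SAP Appendix A gives the code. It requests "PROC PHREG covs(aggregate" (a sandwich variance summed by subject) and fits "MODEL (Tstart,Tstop)*Status(0)=Txgrp / ties=efron", with treatment as the only term. It asks for no score, exact, permutation or penalised test. Under SAP Section 5, subjects without a qualifying bleed stay in the risk set: "These subjects will be included in analysis with" a censored status. None of these places says what happens if one arm has no event.

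**The concern.** A p-value that can open a confirmatory test should be valid for any data the trial may plausibly produce. The placebo arm has 54 subjects. The bleeding window runs from study day 1 to 30 days after the last dose: with 7–21 weeks of dosing, 49 + 30 = 79 to 147 + 30 = 177 days. Under Protocol 9.2.2.2, bleeds reported but not visible at the visit are graded 1, which lowers the grade ≥2 count. An arm with no event cannot be ruled out.

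In that case the robust Wald test does not merely become approximate. It reports overwhelming significance from one or two events, with a tight interval around a meaningless hazard ratio. Suppose romiplostim truly improves the first three endpoints but not bleeding. A false rejection here is then itself a family-wise error, so the stated control below 0.05 would not hold.

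**Working it through.** **Inputs.** From the documents: 162 subjects, 108 romiplostim and 54 placebo, 6 randomisation strata (3 tumour types × 2 platelet levels), 2-sided 0.05, model and code as above. Assumed: the grade ≥2 rate, which the documents do not give. The nearest figure is 3 of 22 (14%) with bleeding of unstated grade in a retrospective review (Protocol 3.2.4.2). The range used is 0.005 to 0.14 bleeds per subject.

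**1. The plan's own figure.** There is none for bleeding. The one stated power, 93% for the primary endpoint, reproduces: p² + ρp(1−p) gives 0.09 + 0.7×0.21 = 0.237 and 0.36 + 0.7×0.24 = 0.528, odds ratio 3.6. A simulated stratified CMH test with continuity correction then has 93.3% power.

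**2. Why the statistic breaks.** Take d bleeds in d different placebo subjects and none on romiplostim, with n₁ and n₀ subjects at risk. The fitted probability that a bleed belongs to romiplostim is w ≈ (n₁/n₀)e^β for very negative β.
- Information ≈ d·w.
- Sum of squared score residuals ≈ d·w², plus small terms.
- Robust variance ≈ d·w²/(d·w)² = 1/d.

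The factor e^β cancels. The standard error settles near √(1/d), that is 1.00, 0.71 and 0.58 for d = 1, 2 and 3, while β runs on until the iteration stops.

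**3. Fits** (R `coxph`, Efron ties, 6 strata, clustered by subject). The exact p is binomial, with placebo share 1/3.

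| Bleeds (placebo / romiplostim) | β | robust SE | z | robust Wald p | robust score p | exact p |
|---|---|---|---|---|---|---|
| 1 / 0 | −21.15 | 0.984 | −21.5 | 2e-102 | 0.31 | 1/3 = 0.33 |
| 2 / 0 | −21.15 | 0.689 | −30.7 | 4e-207 | 0.147 | 1/9 = 0.11 |
| 3 / 0 | −21.15 | 0.564 | −37.5 | 2e-307 | 0.076 | 1/27 = 0.037 |
| 0 / 2 | +19.67 | 0.718 | 27.4 | 3e-165 | 0.157 | 1.00 |
| 2 / 1 | −1.39 | 1.199 | −1.16 | 0.25 | 0.31 | 7/27 = 0.26 |

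A separate coding with a relative-gradient stop of 1e-8, taken as the PHREG default, gave β −19.15, SE 0.672 and p = 1e-178 for 2 / 0. PHREG itself was not run. The exact power of ten depends on the stopping rule; the conclusion does not. One bleed in the other arm removes the artefact. For 2 / 0 the remaining candidates straddle 0.05: likelihood ratio 0.036, model-based score 0.046, model-based Wald 0.999.

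**4. How often, under no effect.** With Poisson rate λ per subject:
- placebo only: e^(−108λ)(1 − e^(−54λ))
- romiplostim only: e^(−54λ)(1 − e^(−108λ))

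At λ = 0.01 these are 0.340×0.417 = 14.2% and 0.583×0.660 = 38.5%, total 52.7%.

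| λ | expected bleeds | all in one arm | all in placebo |
|---|---|---|---|
| 0.005 | 0.8 | 45.6% | 13.8% |
| 0.01 | 1.6 | 52.7% | 14.2% |
| 0.02 | 3.2 | 37.7% | 7.6% |
| 0.03 | 4.9 | 22.2% | 3.1% |
| 0.05 | 8.1 | 7.1% | 0.4% |
| 0.10 | 16.2 | 0.5% | about 0 |
| 0.14 | 22.7 | 0.05% | about 0 |

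**5. Simulated rejection by the robust Wald test.** Two simulations under no effect agree: 53–54%, 38–39%, 23–25% and 9–10% at 0.01, 0.02, 0.03 and 0.05, and 5–6% from 0.08 upwards. One was indexed by bleeds per subject. The other was indexed by the share of subjects with a bleed and used 2,500 trials per setting, windows of 79–177 days, gamma frailty variance 1 and assumed permuted blocks. In the latter, rejections favouring romiplostim were 15.5%, 6.7%, 4.3% and 2.4%, against a nominal 2.5%. A re-randomisation test held 3.7–5.8% overall.

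**The case against.** The strongest reply is that the documents never say Wald. They say only that the model supplies a p-value, and a robust score test on the 2 / 0 data gives 0.147 and leaves the gate shut. This stands as a limit on what can be called documented. It does not remove the problem: the Appendix A code's usual p-value beside the hazard ratio is the robust Wald one, and an unnamed choice among tests giving about 0, 0.036, 0.046, 0.11 and 0.147 decides the gate.

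Second, bleeds may not be sparse. At the 14% seen in the retrospective review the problem vanishes. This also stands, but that figure is for any grade in 22 patients, and no grade ≥2 rate is given.

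Third, the excess in romiplostim's favour is narrow. With three placebo bleeds and none on romiplostim an exact test also rejects. With one bleed per subject the decisions therefore differ in that direction only at one or two bleeds, both on placebo if two: null probability 13.6%, 6.4%, 2.2% and 0.2% at rates of 1%, 2%, 3% and 5%. This is correct. Most null rejections point to harm, because 2:1 allocation makes an empty placebo arm the likelier case. They still count, since the gate has no direction.

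Fourth, SAP 8.6 permits alternative methods if distributional assumptions fail, and event counts by arm will be shown. But 8.6 is permissive and names neither trigger nor test, whereas the nadir endpoint has a stepwise fallback (SAP 9.5.2.1). A choice made after seeing a 2 / 0 split would not be pre-specified.

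**Conclusion.** The point holds conditionally. As coded, the bleeding p-value is unusable for gating when all informative bleeds lie in one arm. The consequence for overall survival rests on four conditions:
- The reported p-value is the robust Wald one, which is inferred from the code.
- At least one bleed occurs in a stratum where both arms are at risk; otherwise the effect is not estimable.
- The primary, nadir and time-to-response tests have already been rejected.
- Bleeds are few: the effect is large at about 5 or fewer in total and negligible at about 16 or more.

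Three stronger readings are tempting, and the documents do not support them. A reader might infer that two placebo bleeds against none would by themselves pass the gate, but bleeding is fourth in the whole chain. A reader might take 53% or 38% as the risk of a false benefit claim, but the benefit share is about 15% and 7–8%, and both depend on an assumed rate. A reader might say error control fails when romiplostim abolishes bleeding, but if the drug truly prevents bleeds the null is false and rejecting it is no type I error. In that case the defect is the meaningless hazard ratio and interval.

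**What to change.** In SAP 9.5.2.3 and Appendix A, name the gating test: a re-randomisation test of the Andersen-Gill score statistic that permutes treatment within the 6 randomisation strata and moves each subject's events together, so that repeat bleeds stay clustered. State that the robust Wald p-value is not used for gating.

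Add a zero-event rule: if either arm has no grade ≥2 bleed, the Wald hazard ratio and confidence interval are not reported as estimates, and event counts and rates by arm are given instead.

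Record the change in SAP Section 10, which now states that nothing departs from the protocol, and settle it before unblinding. The cost is this wording and a few lines of code; no new data are needed. The drawback is that the permutation p-value is slightly conservative when events are few.
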